### **Sample size calculation**

Sample size calculation was calculated based on long delay recall score as the main observation index. As this study adopts a new treatment method, sample size was acquired from our preliminary study. As a result, the mean (5.1) and standard deviation (2.23) after treatment, as well as the mean (2.6) after false stimulation, a minimum total sample size of 33 treatment-completers was required to achieve 90% power at  $\alpha=0.05$ . To account for attrition and ensure adequate power at 2 weeks after treatment, 42 participants need to be included, with 21 subjects in each group.

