## **Test grouping**

Patients with aMCI will be randomly allocated (1:1) to groups receiving either ccPAS or sham stimulation by personnel external to the clinical team using a computer-based algorithm.

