## **Research process**

This study is mainly divided into three parts. First, identify the stimulation

---

targets related to long-term delayed recall; Second, intervene the stimulation target and observe the effect in patients with aMCI; Third, explore the relationship between the clinical efficacy and function of the stimulated brain region. Specifically, it is divided into the following six points: 1. In 21 healthy controls, the “cortex-hippocampus” network with white matter fiber connection will be identified based on probabilistic fiber tracking and segmentation techniques; 2. In the white matter based “cortex-hippocampus” network, identify the long-term delayed recall related to “cortex-hippocampus” functional connectivity in 42 patients with aMCI, and select the most relevant functional connectivity that TMS can stimulate as the stimulation target. 3. 42 patients with aMCI will be randomly divided into two groups (treatment group and sham stimulation group), and the stimulation targets on individual space will be calculated in each subject. 4. The TMS protocol and the sham stimulation protocol will be implemented in patients with aMCI. 5. The changes of cognitive function between the sham stimulation group and the treatment group before and after intervention will be compared. 6. The changes of fMRI between the sham stimulation group and the treatment group before and after intervention will be compared, as well as the impact of the changes on cognitive function.

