## Statistical analysis

SPSS 21.0 (SPSS Inc., Chicago, Illinois) software will be used for statistical analysis in clinical data. The statistical description of measurement data is expressed by mean  $\pm$  standard deviation. The comparison of the two groups of mean: when it conforms to the normal distribution and homogeneity test of variance, the independent sample t test is used.

The stimulation targets related to long-term delayed recall will be identified by analyzing the relationship between FC of “cortex-hippocampus” circuit and AVLT long delayed memory performance in aMCI patients. Using the left hippocampus as the seed point, ROI based FC analysis to the cortical brain area of the “cortex-hippocampus” network will be calculated. A generalized linear model will be constructed with AVLT\_N5 score as dependent variable and every FC value of left “hippocampus-cortex” network as independent variable.

The repeated measurement ANOVA will be performed in comparison between the treatment group and sham stimulation group before and after treatment, the test of intra subject effect will be corrected by Greenhouse-Geisser, and the post test will be performed by LSD method. Effect sizes (Cohen’s d) will be interpreted as small = 0.2, medium = 0.5, large = 0.8. Non parametric test shall be adopted when it does not

---

conform to normal distribution or homogeneity of variance. The counting data will be expressed by frequency/rate, and the comparison between the two groups will be made by chi square test or Fisher exact probability method. The  $p < 0.05$  (two-sided) indicates significant statistical difference. GraphPad Prism 6 will be used for drawing.

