The statistical analysis of magnetic resonance data will be carried out using Matlab2013b, SPM12, GRETNA and the Resting State fMRI Data Analysis Toolkit (REST version 1.8). The flexible factorial of the second order analysis will be used to design the statistical matrix, and the three factors of subjects, grouping and time are set, in which grouping and time are fixed factors, and the number of subjects is random factors, and then the main effect and grouping $\times$  the time interaction matrix are set respectively for statistical analysis, and then post hoc analysis will be done. The results will be reported using bspmview software, and the names of brain regions will be referred to AAL template. BrainNetView and GraphPad Prism 6 are used for drawing. For correlation analysis, a generalized linear model will be fitted with the delta AVLT\_N5 as the dependent variable and the delta FC value between left hippocampus and left precuneus as independent variables, using age and years of education as covariates.

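### If the main effect planned for the fMRI maps includes group, the flexible factorial tests it against within-subject error and gives too many false positives

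*Protocol*

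**What the plan says.** Under Statistical analysis, the imaging data are analysed with SPM12 among other tools, and the second-level model is fixed: "The flexible factorial of the second order analysis will be used to design the statistical matrix". Its factors are listed ("the three factors of subjects, grouping and time are set") and given a status: "grouping and time are fixed factors, and the number of subjects is random factors, and then the main effect". The same sentence adds the group-by-time interaction and then post hoc analysis. It does not say which factor the main effect belongs to. It names no error term, and no separate between-subject model is planned for group.

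Under Test grouping, group is a between-subject factor: "Patients with aMCI will be randomly allocated (1:1) to groups receiving either ccPAS or sham stimulation". The sixth point under Research process gives the imaging question: "The changes of fMRI between the sham stimulation group and the treatment group before and after intervention will be compared". The planned size is in Sample size calculation: "42 participants need to be included, with 21 subjects in each group".

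**The concern.** In a parallel-group design with repeated scans, two kinds of effect need two different error terms. Time and group by time are comparisons within patients, and the residual left after removing patient effects is the right yardstick for them. The group main effect compares different patients, so its yardstick must include the variation between patients. A flexible factorial with a subject factor has only one residual, the within-patient one. Labelling subject as random does not create a second error stratum in that model.

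If two scans of the same patient are positively correlated, the within-patient residual is too small for a group comparison, and voxels or regions pass the threshold too often. Central reorganization is part of the stated Objective, so a map of group differences obtained this way could be read as an imaging effect of treatment. The contrast is also poorly aimed. Averaged over both scans, it mixes any baseline difference between arms with half of any treatment effect, whereas Research process asks about change.

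**Working it through.** **Plan's own figure.** The protocol gives no error rate or power for the imaging analysis, so there is none to reproduce. Its one computable figure, 33 completers, concerns delayed recall and does not bear on this point.

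**Inputs from the protocol.** Two parallel arms (Test grouping); 21 patients per arm (Sample size calculation); two time points, before and after (Research process); subject, group and time in one model (Statistical analysis).

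**Assumed inputs.** The correlation ρ between a patient's two scans is not given; 0.2 to 0.8 is used as a range. The nominal level is also assumed. The 0.05 rule ("two-sided) indicates significant statistical difference") follows the clinical-data text, and no separate imaging threshold is stated.

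**Step 1: residual degrees of freedom.** There are 42 × 2 = 84 scans. The design with subject columns and the four group-by-time cells has rank 44, so the residual has 84 − 44 = 40 df. All of it is within-subject.

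**Step 2: variance of the group contrast.** Let σ² be the variance of one scan. A patient's mean over two scans has variance σ²(1+ρ)/2. The difference d between two arm means of 21 patients has variance 2 × σ²(1+ρ)/(2 × 21) = σ²(1+ρ)/21.

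**Step 3: what the model uses instead.** The within-subject residual mean square has expectation σ²(1−ρ), so the model takes the variance of d to be σ²(1−ρ)/21. Under the null, the group F statistic is therefore (1+ρ)/(1−ρ) times an F(1,40) variable.

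**Step 4: true type I error.** It equals P(|t40| > c / √[(1+ρ)/(1−ρ)]), where c is the two-sided critical value, 2.021 at 0.05. For ρ = 0.5 the ratio is 1.5/0.5 = 3, the effective cut-off is 2.021/1.732 = 1.167, and the probability is 0.250.

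| ρ (assumed) | (1+ρ)/(1−ρ) | true rate at nominal 0.05 | true rate at nominal 0.001 |
|---|---|---|---|
| 0 | 1.00 | 0.050 | 0.001 |
| 0.2 | 1.50 | 0.107 | 0.006 |
| 0.3 | 1.86 | 0.146 | 0.013 |
| 0.5 | 3.00 | 0.250 | 0.047 |
| 0.7 | 5.67 | 0.401 | 0.144 |
| 0.8 | 9.00 | 0.504 | 0.244 |

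A stricter voxel threshold does not help. At 0.001 the rate is about 13 to 144 times nominal for ρ from 0.3 to 0.7. With 33 completers (31 df) the rates at nominal 0.05 barely move: 0.145, 0.248 and 0.398 for ρ = 0.3, 0.5 and 0.7.

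**Step 5: simulation check.** With 40,000 null trials per ρ, the group test against the within-subject residual rejects in 0.145, 0.247 and 0.400 for ρ = 0.3, 0.5 and 0.7. In the same trials, group by time rejects in 0.048 to 0.052 and time in 0.048 to 0.050. The group effect tested on patient means with between-subject error rejects in 0.049.

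**Step 6: post hoc comparisons.** A comparison of the arms at one time point has variance 2σ²/21. The same residual takes it to be 2σ²(1−ρ)/21, so the inflation factor is 1/(1−ρ). The true type I error at nominal 0.05 is 0.099, 0.161 and 0.275 for ρ = 0.3, 0.5 and 0.7.

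**Step 7: subject columns left out.** With one pooled residual (84 − 4 = 80 df) and no correlation modelled, the simulated rate for the group main effect is 0.084, 0.111 and 0.132 for the same ρ.

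**The case against.** The strongest reply is that the contrast is inferred. The text speaks of one main effect and names no factor. If time alone was meant, its test against this residual is correct and the problem with the main-effect contrast does not arise. This stands as a limit. But group and time are introduced together as the two fixed factors immediately before the main effect, and nothing restricts it to time.

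Second, the result depends on how the model is set up. With subject columns present, a plain group contrast is not estimable; it becomes so only with weights on those columns. Without them the inflation is smaller. This is also true, but each route that yields a group test from a single uncorrected residual is too liberal. A SAP may give the contrasts in detail. The protocol nevertheless already fixes the model, its factors and the type of contrasts, and the problem lies in that combination.

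Third, the treatment question is already served. Group by time is planned alongside, it is the comparison that Research process asks for, and its test is valid. That is right, and it rules out one stronger reading a reader might draw, that the imaging comparison of treatment as a whole is invalid. The regression of change in recall on change in FC does not use this residual, and the primary outcome is a cognitive score.

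A reader might also infer that most regions flagged for group would be artefacts. The documents do not support this. The rates above hold under the null, and the share of false findings among flagged regions depends on true effects that are unknown here. Nor does the protocol say that group regions in particular feed the post hoc tests, or that they would be reported as reorganization.

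**Conclusion.** The point holds in a limited form. On the natural reading, the plan tests a between-subject group effect on fMRI maps against within-subject error. The true type I error is then about 0.15 to 0.40 instead of 0.05 for ρ from 0.3 to 0.7, or about 0.08 to 0.13 if subject columns are omitted and correlation is ignored. Post hoc comparisons of the arms at a single time point that use the within-subject residual are inflated too, to about 0.10 to 0.28. The size rests on an assumed ρ and an assumed nominal level; the direction requires only ρ above zero. The finding is confined to group main-effect maps and such post hoc comparisons. Imaging maps are not listed among the primary or secondary outcomes, and the trial is a pilot, so this is a matter to correct in the analysis text and not a threat to the main result.

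**What to change.** Use the flexible factorial only for time and group by time, and say so. Base the fMRI treatment inference on group by time, which with two scans is equivalent to a two-sample test on post-minus-pre maps. Drop the group main effect. If an overall group effect is wanted, test it in a separate two-sample model on each patient's mean map. If a comparison at one time point is wanted, use a two-sample model on the maps at that time point. Both then use between-subject error. If only the time main effect was meant, naming it settles the main-effect contrast, and the post hoc comparisons of the arms still need the separate model.

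The cost is contrast and model specification only. No data collection, sample size or primary analysis changes.

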### **ccPAS Procedure**

Treatment will be delivered with a MagPro X100 stimulator equipped with the B70 fluid-cooled coil (MagVenture). The maximum surface magnetic field intensity of the coil is 4.2T. All patients will receive 10 interventions (5 times a week for two weeks). Each patient’s resting motor threshold (RMT) will be determined in accordance with standard clinical practice.

**Treatment group:** two B70 fluid-cooled coils will be needed for the ccPAS in left prefrontal lobe and left precuneus. The ccPAS consisted of 5-Hz stimulation and a total of 900 pairs pulses, the interval of each pair stimulation at two stimulation targets is 2ms. First, 80% RMT will be given to the left prefrontal lobe, and then 120% RMT will be given to the left precuneus. Five times a week for two consecutive weeks.

---

**Sham stimulation group:** the two coils will be placed vertically on the scalp of the patients, and the stimulation parameters will be the same as those in the treatment group. The sound generated by the coil simulating, and the method has virtually no effect on the cerebral cortex. Other parts are the same as the treatment group.

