## Outcome

1. The primary outcome is change from baseline in long-term delayed recall performance (Delta AVLT\_N5) following the ccPAS intervention compared with the sham stimulation group.
2. Secondary outcome measures is also recorded as the primary outcome, included MMSE, other AVLT items, STT, SDMT, BNT, CFT. In exploratory analyses, we will assess the relationship of changes in cognitive performance and FC.

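### The exploratory model relating change in connectivity to change in delayed recall leaves out treatment arm, so if both arms are pooled an association could appear with none within either arm

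*Protocol*

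**What the plan says.** The model is described at the end of the magnetic resonance part of the Protocol's Statistical analysis section. It states that "a generalized linear model will be fitted with the delta AVLT"_N5 score as dependent variable, and the right-hand side is "the delta FC value between left hippocampus and left precuneus as independent variables, using age and years of education as covariates". Neither treatment arm nor an arm-by-FC term is listed. The flexible factorial model described just before it does include group as a factor.

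Three other sections bear on how to read this model:

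- Research process gives the third part of the study as to "explore the relationship between the clinical efficacy and function of the stimulated brain region". Its step 6 compares fMRI changes between the sham and treatment groups, "as well as the impact of the changes on cognitive function".
- Outcome sets the status: "In exploratory analyses, we will assess the relationship of changes in cognitive performance and FC". The same section makes change in AVLT_N5 the primary outcome.
- ccPAS Procedure describes "ccPAS in left prefrontal lobe and left precuneus", so one end of the FC predictor is a stimulated site.

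No section says which patients enter the model.

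**The concern.** Change in AVLT_N5 is what ccPAS is meant to improve, and hippocampus-precuneus FC is a connection it is meant to alter. If the treatment does both, arm is a common cause of the two change scores. A regression over both arms without arm then has a slope made of two parts. One is the relation between patients within an arm, which is the quantity of interest. The other is the line joining the two arm means, which is non-zero whenever ccPAS moves both variables, however unrelated the two changes are. Randomisation does not remove the second part, because it balances the arms at baseline and not after treatment.

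At stake is the interpretation of the third part of the study. A significant pooled slope could be read as evidence that patients whose circuit changed more also recalled more, when it might only restate that the arms differ on both measures.

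**Working it through.** **Inputs from the Protocol.** Sample size calculation: "the mean (5.1) and standard deviation (2.23) after treatment", a mean of 2.6 after sham, 90% power, alpha 0.05, 33 completers, 42 enrolled with 21 per group. Test grouping: 1:1 allocation. Statistical analysis: two-sided testing.

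**Assumed, not in the Protocol.** The arm effect on FC change, taken over 0 to 1.12 SD. The SD of the AVLT_N5 change score: 2.23 is given only for the post-treatment score, and is taken to hold for the change score and in both arms. The generalized linear model is taken as ordinary least squares with normal errors.

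**Step 1. The plan's own figure.** The standardised effect is (5.1 − 2.6)/2.23 = 2.5/2.23 = 1.12. The normal-approximation size per arm is 2 × (1.960 + 1.282)² × (2.23/2.5)² ≈ 16.7, or about 33.4 in total before rounding. That agrees with the stated 33. Going to 42 allows for 1 − 33/42 = 21% attrition. So 1.12 SD is the effect the trial was planned on.

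**Step 2. Correlation produced by pooling alone.** Let dy and dx be the standardised arm effects on AVLT_N5 change and FC change. With 1:1 allocation and zero within-arm correlation, the between-arm covariance is dy·dx/4 and the total variances are 1 + dy²/4 and 1 + dx²/4. Hence

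r = (dy·dx/4) / √[(1 + dy²/4)(1 + dx²/4)].

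For dy = 1.12 and dx = 0.8: 0.224/√(1.314 × 1.160) = 0.224/1.235 = 0.18.

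**Step 3. False-positive rate.** A simulation of 6,000 trials per setting drew independent normal changes within arms and tested the FC coefficient at two-sided 0.05, adjusted for age and education, with and without arm. With dy = 1.12:

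| FC effect dx (SD, assumed) | Pooled r | As written, N=42 | As written, N=33 | With arm, N=42 | With arm, N=33 |
|---|---|---|---|---|---|
| 0 | 0.00 | 5% | 5% | 5% | 5% |
| 0.2 | 0.05 | 6% | 6% | 5% | 5% |
| 0.5 | 0.12 | 11% | 10% | 5% | 5% |
| 0.8 | 0.18 | 21% | 17% | 5% | 5% |
| 1.12 | 0.24 | 33% | 25% | 5% | 5% |

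**Step 4. Sensitivity to the recall effect.** With dy = 0.5 and N=42, the rate as written runs from 5% to 11% over the same FC effects. With dy = 0 it stays near 5%. With arm in the model it lay between 4.5% and 5.5% in every setting run.

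**The case against.** The strongest reply is that pooling is an inference. The analysis set is not stated, and the third part of the study, with its reference to the stimulated brain region, could be read as concerning ccPAS patients only. Fitted in that arm alone, the model would not have this problem. That stands as a limit on certainty. But no section states such a restriction, and step 6 under Research process ties the analysis to changes compared between the two groups. Nor is this just a detail left to a SAP, because the covariates are written out and arm is not among them.

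The size also depends on quantities the Protocol does not give. The FC effect is assumed. The 1.12 SD comes from post-treatment scores, so the effect on the change score may be larger or smaller. If either arm effect is absent, there is no inflation.

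A reader might infer more than the document supports:

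- *That a spurious association will be found.* Even at an FC effect of 1.12 SD with 42 patients, about two trials in three would show no significant slope. The association could appear; it need not.
- *That the third part of the study could be declared successful on this result.* The Protocol labels the analysis exploratory, speaks of exploring the relation, and attaches no success criterion to this model.
- *That the model confuses between-arm and within-patient relations.* Each patient contributes one pair of changes, so no within-patient relation can be estimated. The contrast is with the relation between patients within an arm.
- *That the change scores must be replaced by post-treatment values adjusted for baseline.* That is a matter of preference and is not needed to cure this defect.

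It may also be said that the pooled association is itself of interest, as the path through which treatment acts. But without arm, any two treatment effects look linked. To separate a shared path from two parallel effects, the slope must be conditional on arm.

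**Conclusion.** The point holds in limited form. The covariate list omits arm, both change scores are intended targets of the treatment, and the most natural reading is that both arms are pooled. On that reading the slope is biased as an estimate of the within-arm relation whenever ccPAS moves both variables. At the plan's recall effect, and with no within-arm correlation, the false-positive rate goes from nominal with no FC effect to about a third (N=42) or a quarter (N=33) when the FC effect equals the recall effect. These rates rest on the assumed FC effect, on 2.23 serving as the change-score SD in both arms, and on pooling. The primary comparison and the sample size are unaffected. The change is worth making because it is cheap and decides what the slope means.

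**What to change.** In the last part of Statistical analysis:

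- Add treatment arm to age and years of education as a covariate in the model of AVLT_N5 change on FC change.
- State which patients enter it, for example all randomised patients with both scans and both AVLT_N5 scores. If only the ccPAS arm is meant, say so; arm then drops out of the model.
- Report the FC coefficient from the arm-adjusted model as the within-arm slope, with its confidence interval. Fit the arm-by-FC-change interaction separately as exploratory.

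The model as written estimates four coefficients (intercept, FC change, age, education), leaving 38 residual degrees of freedom with 42 patients or 29 with 33. Adding arm takes one, leaving 37 or 28; the interaction takes one more. There is also some loss of precision when the FC effect is large, because the slope then uses only within-arm variation in FC: at 1.12 SD that is 1/(1 + 1.12²/4) = 1/1.31, or 76%, of the total variance. No new data are needed, only a change of wording.
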